3.4.2.4 Subgroup Analyses

[figure not shown]
The secondary endpoints will be analyzed for the subgroups listed below, which includes a mixture of subgroups defined before and after randomization. As for the primary efficacy endpoint, subgroups defined after randomization will not be used to make comparisons between active and placebo arms.

- Sex: male vs female
- Diabetic vs non-diabetic
- Infarct location: anterior vs non-anterior
- Infarct location: LAD vs non-LAD
- Infarct Location: LAD vs LCX vs. RCA
- TIMI Flow Grade 0 vs 1 vs 2 vs 3 pre-pPCI
- TIMI Flow Grade 0 or 1 vs 2 or 3 pre-pPCI
- TIMI Flow Grade 0 vs 1 vs 2 vs 3 post-pPCI
- TIMI Flow Grade 0 or 1 vs 2 or 3 post-pPCI
- Above vs below the median door-to-device time

- Above vs below the median symptom onset-to-device time
- Above vs below the median symptom onset-to-door time
- Drug administration before vs after pPCI
- Above vs below the median time between dose 1 and pPCI
- Above vs below the median HDL at baseline
- Above vs below the median HDL change from baseline
- Above vs below the median apoA1 at baseline
- Above vs below the median apoA1 change from baseline
- Cardiovascular Event vs No Cardiovascular Event
- HF Hospitalization vs No HF Hospitalization
- Prior statin vs statin naïve
- Baseline LDL-C \leq 100 vs $>$ 100 mg/dL
- Baseline LDL-C \leq 70 vs $>$ 70 mg/dL

3.4.3 Other Efficacy Analyses

3.5 Pharmacodynamic Endpoint(s) and Analyses

3.5.1.1 Pharmacodynamic Endpoint(s)

The following pharmacodynamic (PD) markers will be collected:

3.5.1.2 Analysis of Pharmacodynamic Endpoint

The PD markers measured at each time point and change from baseline at each post-baseline time point will be summarized using descriptive statistics by treatment group with placebo group combined when appropriate.

3.6 Safety Analyses

3.6.1 Adverse Events and Serious Adverse Events

Safety analysis will be based on the As-treated Population. AE collection begins after randomization and lasts until the end of the study. SAE collection begins after the subject signs the informed consent document and lasts until the end of the study. Adverse events will be coded using the Medical Dictionary for Regulatory Activities (MedDRA) by system organ class (SOC) and preferred term (PT). Specific AEs will be counted once for each subject for calculating rates, but will be presented in total in subject listings. If the same AE occurs multiple times within a particular subject, the highest severity and level of causality will be reported. All treatment-emergent adverse events will be summarized overall and by

MedDRA SOC and PT, by severity and relationship to investigational product. In addition, summaries of deaths, serious adverse events, and treatment discontinuations due to AEs will be provided.

3.6.2 Adverse Events of Special Interest

Not applicable.

3.6.3 Deaths and Treatment Discontinuations due to Adverse Events

Deaths, and AEs leading to discontinuation of investigational product will be summarized.

3.6.4 Clinical Laboratory Evaluation

Clinical laboratory safety tests including serum chemistry and hematology parameters will be summarized using descriptive statistics at each time point by treatment group with placebo group combined when appropriate. Change from baseline to each post-baseline time point in these data will also be summarized, where appropriate. A shift table will be provided for these clinical laboratory parameters where possible.

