4.8.4.2 Analysis of Clinical Laboratory Parameters

Clinical laboratory safety tests including serum chemistry and hematology parameters will be summarized using descriptive statistics at each time point by treatment group with placebo group combined when appropriate. Change from baseline to each post baseline time point in these data will also be summarized, where appropriate. A shift table will be provided for these clinical laboratory parameters as well where possible.

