5.6.2 Hepatic Function Abnormality

Patients with acute STEMI are very likely to show aminotransferase elevations at inclusion, either originating from cardiomyocytes, or, if released from hepatocytes, related to hepatic ischemia or congestion. Definition of potential signals for Drug-Induced Liver Injury and requirements for expedited reporting need to be adapted accordingly. Please refer to Section [10.5](#) for details.

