10.5.2 Definitions

10.5.2.1 Potential serious liver injury corresponding to Hy's Law

- ALT and total bilirubin (TBL) normal at baseline:
ALT $> 3 \times$ upper limit of normal (ULN), with associated elevation in glutamate dehydrogenase (GLDH), without corresponding CK and/or troponin elevation, **together with** TBL $\geq 2 \times$ ULN, at any point during the study following the start of study medication, irrespective of an increase in alkaline phosphatase (ALP).
- ALT or TBIL abnormal at baseline:
ALT $> 3 \times$ baseline or > 300 U/L (whichever occurs first), with associated elevation in GLDH, without corresponding CK and/or troponin elevation, **together with** TBL $\geq 2 \times$ ULN, or, if abnormal at baseline, $> 2 \times$ bsl, at any point during the study following the start of study medication, irrespective of an increase in alkaline phosphatase (ALP).

If ALT is decreasing from baseline, nadir will be new baseline

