10.6 Appendix 6 - Management of Liver Toxicity

In the setting of acute MI, transaminases used to monitor for liver toxicity (ALT and AST) can be elevated and of cardiac origin. [Table 14](#) describes actions to be taken according to ALT; GLDH; total bilirubin; and subject symptoms.

Table 14 Actions to be Taken According to ALT, Glutamate Dehydrogenase, Total Bilirubin

Treatment-emergent ALT		Treatment-emergent TBL	Liver Symptoms	Action
1	If normal at baseline: ALT > 3 x ULN, with associated elevation in GLDH, without corresponding CK and troponin elevation	Normal	None	Repeat ALT, AST, ALP, TBL, in 24-48 hours Follow-up for symptoms.
	If abnormal at baseline: ALT > 2 x baseline or > 200 U/L (whichever occurs first), with associated elevation in GLDH, without corresponding CK and troponin elevation If ALT is decreasing from baseline, nadir will be new baseline.	For patients with abnormal bsl, No change in baseline TBL		

Table 14 Actions to be Taken According to ALT, Glutamate Dehydrogenase, Total Bilirubin

Treatment-emergent ALT		Treatment-emergent TBL	Liver Symptoms	Action
2	If normal at baseline: ALT > 5 x ULN, with associated elevation in GLDH, without corresponding CK and troponin elevation	Normal	None	Interrupt study drug. Initiate close monitoring and workup for competing etiologies.
	If abnormal at baseline: ALT > 3 x baseline or > 300 U/L (whichever occurs first), with associated elevation in GLDH, without corresponding CK and troponin elevation If ALT is decreasing from baseline, nadir will be new baseline	For patients with abnormal bsl, No change in baseline TBL		Study drug can be restarted only if another etiology is identified and liver enzymes return to baseline.
3	If normal at baseline: ALT > 3 x ULN, with associated elevation in GLDH, without corresponding CK and troponin elevation	TBL > 2 x ULN	None	Interrupt study drug. Initiate close monitoring and workup for competing etiologies.
	If abnormal at baseline: ALT > 2 x baseline or > 200 U/L (whichever occurs first), with associated elevation in GLDH, without corresponding CK and troponin elevation If ALT is decreasing from baseline, nadir will be new baseline.	For patients with abnormal bsl, > 2 x bsl		Study drug can be restarted only if another etiology is identified and liver enzymes return to baseline.

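### The SAP has no by-arm tabulation of the protocol's own GLDH/CK/troponin-qualified liver criteria, so its laboratory tables are less sensitive to liver-origin ALT rises below a reported SAE

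*SAP*

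**What the plan says.** **Laboratory analysis.** SAP 3.6.4 states that "Clinical laboratory safety tests including serum chemistry and hematology parameters will be summarized using descriptive statistics at each time point by treatment group". It adds change from baseline and a shift table: "A shift table will be provided for these clinical laboratory parameters where possible". Protocol 4.8.4.2 has the same content: "Change from baseline to each post baseline time point in these data will also be summarized, where appropriate", and "A shift table will be provided for these clinical laboratory parameters as well where possible". SAP 3.1 fixes baseline as the last valid value before the first dose on Day 1. For adverse events of special interest, the whole entry in SAP 3.6.2 is "Not applicable".

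**The protocol's warning.** Protocol 5.6.2 says "Patients with acute STEMI are very likely to show aminotransferase elevations at inclusion" and that signal definitions for drug-induced liver injury have to be adapted for this. Appendix 6 (10.6) repeats that "transaminases used to monitor for liver toxicity (ALT and AST) can be elevated and of cardiac origin".

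**The adapted rule.** Appendix 5 (10.5.2.1) qualifies the ALT criterion "with associated elevation in glutamate dehydrogenase (GLDH), without corresponding CK and/or troponin elevation" and combines it with a bilirubin criterion. It resets the ALT reference to the nadir when ALT is falling. Table 14 in Appendix 6 uses a similar qualified ALT criterion, including two rows with normal or unchanged bilirubin and no symptoms.

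**The markers.** GLDH, CK and troponin share the serum chemistry row in the schedules of procedures (Tables 8 and 9). Table 8 places these draws before PCI and on Days 3, 17, 31 and 70-84.

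**The concern.** The protocol recognises that a raised ALT in this population does not by itself point to the liver. It collects three extra markers and writes a joint rule that uses them. The planned aggregate analysis then returns to one variable at a time. A joint within-subject condition cannot be recovered from separate summaries of ALT, GLDH, CK and troponin, even if all four are tabulated.

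The reference values also differ. A subject whose ALT is high on Day 1, falls, and then rises again to a level still below the Day 1 value may meet the protocol's nadir-based criterion. That subject would show no worsening in a shift table built on Day 1.

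What is at stake is how well the study report can show a modest liver-origin imbalance between arms, in a Phase 2b trial meant to inform further development.

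**Working it through.** **No figure to reproduce.** The documents state no rate, threshold, sample size or power for a liver comparison. The check is textual, with an illustration on assumed rates.

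**Step 1: where each type of finding would appear.**

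| Finding in a subject | Case-level route | By-arm table in the SAP |
|---|---|---|
| Qualified ALT rise plus bilirubin criterion, no other explanation agreed | Central laboratory alert, review, reported as an SAE (10.5.3 to 10.5.5) | SAE summaries (SAP 3.6.1) |
| ALT with GLDH rise, normal bilirubin, judged medically significant or needing intervention | Alert; reported as an AE (Protocol 5.2) | AE summaries |
| ALT with GLDH rise, normal bilirubin, judged neither | Alert; not to be reported as an AE (Protocol 5.2) | Only inside the one-variable laboratory tables |

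The third row is the gap. The summary of AEs leading to discontinuation does not close it: it too depends on AE reporting, and Cohort A dosing ends with the Day 3 dose (Protocol 3.1.2), so a later rise there cannot lead to discontinuation.

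**Step 2: why background matters.** Let p0 be the share of placebo subjects flagged by a definition, and d the drug-caused excess among those not otherwise flagged. The active rate is p1 = p0 + d(1 − p0). Both p0 and d are assumptions. Arm sizes are the planned pooled numbers in Protocol 3.1.2: 2 × 180 = 360 on MEDI6012 and 2 × 90 = 180 on placebo. Example: p0 = 0.40 and d = 0.03 give p1 = 0.40 + 0.03 × 0.60 = 0.418. Exact power of a one-sided 0.05 Fisher test:

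| p0 | d = 2% | d = 3% | d = 5% |
|---|---|---|---|
| 1% | 29% | 55% | 89% |
| 5% | 16% | 28% | 57% |
| 10% | 12% | 19% | 38% |
| 20% | 9% | 13% | 24% |
| 40% | 7% | 9% | 14% |

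The SAP plans no such test. Power serves here only as a yardstick for how visible an excess would be.

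**Step 3: how far the gain depends on assumptions.** The 1% row describes the joint rule only if the rule catches every drug-caused rise. If it caught two thirds, a 3% excess would become 0.03 × 2/3 = 0.02, and power would be 29% instead of 55%. Plain ALT at later visits, if its background had fallen to 5%, would have 28% for the same 3% excess. On those two assumptions the joint rule gains almost nothing. With full sensitivity and a 40% ALT background, the contrast is 55% against 9%.

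**Step 4: the offset if the drug works.** Assume cardiac ALT elevation in 50% of placebo subjects and d = 3%. With no effect on the infarct, the active rate is 0.50 + 0.50 × 0.03 = 51.5%. The active cardiac share c that brings the total back to 50% solves c + (1 − c) × 0.03 = 0.50. So c = 0.47/0.97 = 48.5%, a relative cut of about 3%. A 10% cut gives 0.45 + 0.55 × 0.03 = 46.7%, below placebo despite the liver effect.

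**The case against.** **Liver monitoring is more than ALT and AST tables.** This stands. A reader might infer that transaminase summaries are the only planned liver analysis and that a drug signal would be buried. The documents do not support that. The chemistry panel in Protocol 4.3.4 also contains bilirubin, ALP and gamma glutamyl transferase. The joint rule is applied subject by subject, with SAE reporting as the default when assessment is delayed beyond 12 days. The data monitoring committee can merge treatment codes with study data during the trial.

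**Later visits are already summarised.** This stands. Day 3 is the post-dose draw closest to the infarct, and the plan reports every time point. A subject already raised at inclusion also cannot show a normal-to-high shift.

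**Randomisation balances cardiac release.** This stands unless MEDI6012 changes infarct size. A reader might infer that liver harm would appear as a benefit. That follows only if the drug works and reduces cardiac ALT release enough. Otherwise the effect is noise, not bias.

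**The SAP may not be the last word.** SAP section 1 defers table templates and specifications to a statistical programming plan that is not available here, and a hepatic table could be there. SAP 3.6.4 does not exclude GLDH, CK and troponin, but it does not name them, and Protocol 4.3.4 lists them apart from serum chemistry. The SAP itself makes no commitment to the protocol's criteria.

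**Earlier studies gave no liver warning.** Protocol 1.4.2 reports no clinically relevant changes in standard safety laboratory parameters in the two Phase 2a studies of MEDI6012. This lowers the urgency but does not close the gap.

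**Conclusion.** The point holds in a limited form. The protocol defines marker-qualified liver criteria with a nadir reference, and the SAP tabulates none of them by arm. Serious cases still reach the report through SAE summaries. What is weakened is the view of ALT with GLDH rises at normal bilirubin that never become adverse events.

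The size of the loss cannot be taken from the documents. The background rate, the drug excess and the sensitivity of the joint rule are all assumptions, and the 360 v 180 split is the planned one, before Protocol 4.2.1.1 moved remaining enrolment to 1:1 in Cohort B. A more specific definition helps most where cardiac background is high, and may add little at later visits where it is low. The offset from a smaller infarct is conditional on efficacy. A reader might take the power contrast as a measured deficiency, but it shows only the direction and how the gain varies.

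This is a worthwhile, cheap improvement to the safety tables. It does not show that the trial would miss serious liver injury.

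**What to change.** **Reconcile first.** Before programming, the sponsor must reconcile two differences between Appendix 5 (10.5.2) and Table 14. The exclusion is CK and/or troponin elevation in one and CK and troponin elevation in the other. The bilirubin threshold is at least 2 × ULN in one and above 2 × ULN in the other. This review does not say which is right.

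**Then add to SAP 3.6.4**, for the As-treated Population, pooled MEDI6012 v pooled placebo and by regimen, the number and percentage of subjects ever meeting:

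1. the ALT criterion with GLDH elevation and without CK/troponin elevation;
2. the same together with the bilirubin criterion;
3. the bilirubin criterion alone.

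Use the protocol's nadir reference for ALT. Keep the existing shift tables, with Day 3 labelled as confounded by the infarct. If the statistical programming plan already holds such a table, a cross-reference in the SAP is enough.

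**Cost.** SAP wording and one or two derived tables from data already collected, with no change to patient management. One limit should be stated in the table notes: the joint rule will miss liver rises that occur while CK or troponin is still raised by the infarct.

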3.6.4.1 Vital Signs

Vital sign results will be summarized using descriptive statistics at each time point by treatment group.

3.6.4.2 Electrocardiogram

Not applicable.

3.7 Immunogenicity

Anti-drug antibody (ADA) incidence rate and titer will be tabulated for each treatment group. Samples confirmed positive for ADA will be tested and analyzed for neutralizing antibodies and summarized similarly.

3.8 Pharmacokinetics

Serum MEDI6012 mass concentration time profiles will be summarized for MEDI6012-treated subjects by dose cohort by visit.

Additional PK analyses may be conducted as appropriate. Data obtained in this study may be pooled with other MEDI6012 studies to perform population PK analysis and/or PK/PD analysis.

3.9 COVID-19 Analyses

COVID-19 study disruptions may be summarized if applicable.

Additional analyses may be performed to explore the impact of COVID-19 and implemented contingency measures (eg, subjects discontinued from study treatment and/or study, protocol deviations related to COVID-19) on the safety and efficacy results reported for the study.

In addition, listings may be provided for

- subjects affected by the COVID-19 pandemic
- subjects with reported issues in the clinical trial management system due to COVID-19 pandemic

4 INTERIM ANALYSIS

Two interim analyses are planned. The objectives of the first interim analysis will be to assess futility and potentially to drop a dose regimen. The analysis, which will be conducted after 30% of the Primary Efficacy Analysis Population (assumed 40% rate of exclusion from the primary efficacy analysis population is expected due to TFG 2 or 3 flow in the infarct-related artery on initial angiography and other reasons for subsequent exclusion or drop-out) based on the original sample size ($N = 74$) is enrolled, will require that $> 50\%$ of subjects ($N > 37$) have acute anterior STEMI and have completed their final study visit. The first interim analysis will be conducted through the Independent Data Monitoring Committee (IDMC). The second interim analysis is planned to accelerate decision on future development options for MEDI6012 and will be performed once 60% of the Primary Efficacy Analysis Population (assumed 50% rate of exclusion from the primary efficacy analysis population is expected due to TFG 2 or 3 flow in the infarct-related artery on initial angiography and other reasons for subsequent exclusion or drop-out) based on the revised sample size ($N = 162$) is enrolled and will require that $> 50\%$ of subjects ($N > 81$) have acute anterior STEMI and have completed their final study visit. Details of the second interim analyses will be specified in the unblinding plan. The sponsor and Principal Investigator will monitor the statistical assumptions in a blinded fashion and schedule the interim analyses accordingly.

The assessment of futility will be based on predictive power, which is conditional power averaged over the distribution of the observed treatment effect at the time of interim analysis. The futility analysis will include all available data at the time of the interim data cut.

The predictive power based on the empirical trend observed at the interim analysis will be calculated by

$$\text{predictive power } pp = \Phi\left(\frac{z_\tau - z_{1-\alpha/2}\sqrt{\tau}}{\sqrt{1-\tau}}\right)$$

τ is the information fraction at the interim analysis, z_τ is the observed value of the test statistic at the interim, α is the two-sided significance level at the final analysis based on the original protocol, and Φ is the standardized normal density function.

Each MEDI6012 dose regimen will be compared to the combined placebo group (pooled over dose regimens).

The study may be declared as “futile” if for both the 2-dose and the [redacted] regimens the calculated predictive power is < 20% for

- infarct size in the Primary Efficacy Analysis Population; AND
- ejection fraction in the Primary Efficacy Analysis Population; AND
- infarct size in the Efficacy Analysis Population - TIMI 0-3; AND
- ejection fraction in the Efficacy Analysis Population - TIMI 0-3.

The [redacted] regimen may be dropped if the calculated predictive power is < 20% for

- infarct size in Primary Efficacy Analysis Population; AND
- ejection fraction in Primary Efficacy Analysis Population; AND
- infarct size in Efficacy Analysis Population – TIMI 0-3; AND
- ejection fraction in Efficacy Analysis Population – TIMI 0-3.

For illustration purposes, Figure 4.1 provides the estimated predictive power when the observed infarct size reduction varies from -20 to 50% in the Primary Efficacy Analysis Population. The 20% predictive power translates into an infarct size reduction of approximately 7%. A value of 50% will result in 18% infarct size reduction, which is the minimally detectable treatment effect for this study. Figure 4.2 provides the estimated predictive power when the observed ejection fraction increase varies from a -5 to 10% in the

Primary Efficacy Analysis Population. Calculated predictive power will be based on observed data.

Figure 4.1

Predictive power against observed interim relative infarct size reduction when 30% of the Primary Efficacy Analysis Population is enrolled and complete their final study visit

[figure not shown]
[figure not shown]

Figure 4.2

Predictive power against observed interim ejection fraction increase when 30% of the Primary Efficacy Analysis Population is enrolled and complete their final study visit

Before declaring futility, the IDMC will evaluate data from CTA measurements for plaque regression as well as clinical efficacy endpoints (cardiovascular death, heart failure, myocardial infarction and stroke) and consider these findings in their recommendations regarding futility. If significant benefits for plaque regression and/or clinical outcomes are observed, the IDMC may recommend the data be reviewed by the sponsor's unblinded review committee (URC) for consideration to continue the trial even if the futility criteria for infarct size and ejection fraction are met. Clinical efficacy outcomes will be presented as best-available data [i.e., Clinical Events Committee (CEC) adjudicated + unadjudicated events] as well as CEC adjudicated-only data.

